#### 7.2.2.5.6 Pregnancy and assessments of fertility

Women of childbearing potential must undergo a serum pregnancy test at screening to confirm eligibility in the trial ( $\leq$  4 days before first dose of either study drug), and at EOT. Women of child-bearing potential must additionally undergo a monthly urine pregnancy test during the treatment phase.

In case of pregnancy, the patient must permanently stop study treatment immediately, withdraw from the trial, and the pregnancy must be reported on the Clinical Trial Pregnancy Form.

#### 7.2.2.6 Cardiac assessments

##### 7.2.2.6.1 Electrocardiogram (ECG)

Standard triplicate 12 lead ECG assessments will be performed after the patient has been resting for 5-30 min prior to each time point indicated in [Table 7-2](#) below. The triplicate ECGs should be taken approximately 2 minutes apart. The combined QTcF values from triplicate ECGs will be averaged to provide a single value for each patient. If an abnormal ECG or QTcF value of  $\geq$  481 ms is obtained at any time during the study, study treatment must be interrupted, repeat the ECG measurements and follow management guidelines detailed in [Table 6-5](#).

**Table 7-2 ECG Collection Plan**

Cycle/ Visit 	Day	Time	ECG Type
Screening	-7 to 1	Any time	12 Lead 
1	1	Pre-dose	12-Lead
1	1	2, 4 and 6 h post-dose	12-Lead
1	15	Pre-dose	12 Lead
1	15	2, 4 and 6 h post-dose	12 Lead
2	1	Pre-dose	12 Lead
2	1	2 h post-dose	12 Lead
3	1	Pre-dose	12 Lead
3	1	2 h post-dose	12 Lead
Cycles 4 and subsequent cycles 	1	Pre-dose	12 Lead
End of treatment		Any time	12 Lead
Unscheduled sample		Anytime	12 Lead

Triplicate 12 lead ECG is not required at screening.  
 For C4D1 and subsequent visits, the ECG will be measured only at pre-dose, except when clinically indicated.  
 For patients with QTcF  $\geq$  481ms at any time, interrupt study treatment and follow the procedures described in the "Ribociclib Dose Modification section". If treatment is resumed, repeat ECGs 7 days and 14 days after dose resumption (and then as clinically indicated). During subsequent cycles, perform predose ECG for every cycle, and 2 h post dose starting at every 3rd cycle after thereafter.

The interpretation of the tracing must be made by a qualified physician and documented in the ECG section of the eCRF. Each ECG tracing should be labeled with the study number, patient initials (if permitted by local regulations), Patient Number, date, and kept in the source documents at the study site. Only clinically significant abnormalities should be reported in the Adverse Events eCRF. Clinically significant abnormalities present when the patient signed

informed consent should be reported on the Medical History eCRF page. Clinically significant findings must be discussed with the Novartis Medical Monitor prior to enrolling the patient in the study. New or worsened clinically significant findings occurring after informed consent must be recorded on the Adverse Events eCRF page.

[figure not shown]

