### **1.2.1.2 Clinical experience**

#### **1.2.1.2.1 Clinical safety**

As of 24-Apr-2014, 132 patients have been treated with single agent LEE011 in the FIH phase I study; 85 patients have been treated in the dose escalation part and 47 patients in the dose expansion part of the study.

Patients with advanced solid tumors or lymphomas were treated with increasing doses of LEE011 orally, once daily (qd) for 21 days followed by a 1-week rest (28-day cycle). Doses ranging from 50 mg to 1200 mg were evaluated on this schedule. In addition, continuous dosing of LEE011 at 600 mg was evaluated (qd for 28 days of a 28-day cycle). Treatment has been discontinued in 111 (84%) patients; the primary reasons for treatment discontinuation were: disease progression (96 [72%] patients); AEs (8 [6%] patients); withdrawal of consent (3 [2%] patient); and loss to follow up (1 [1%] patient).

The most frequently reported AEs ( $\geq 10\%$ ), regardless of grade, causality and LEE011 dose were: fatigue (53.8%); nausea (50.8%); neutropenia (47.7%); leukopenia (46.2%); anemia (37.1%); vomiting (34.8%); thrombocytopenia (34.1%); diarrhea (32.6%); lymphopenia (30.3%); decreased appetite, hyperglycemia (21.2% each); constipation (19.7%); hypoalbuminemia (18.9%); dyspnea (18.2%); cough (16.7%); fever, increased creatinine (15.9% each); abdominal pain, AST increase, edema, headache (15.2% each); back pain (14.4%); dizziness (13.6%); ECG QT prolonged (11.4%); blood alkaline phosphatase increased and hypocalcemia (10.6% each).

For either continuous or intermittent dosing, the onset of neutropenia (most frequently Grade 2) occurs by Day 15, reaching a nadir in the third or fourth week with recovery during the week of drug holiday. Some patients require additional time for recovery (7 to 14 days). QT changes become evident in the first cycle by Day 8 and later (once steady state is reached), are associated with the maximum drug levels between 1 to 8 h post-dose, and remain stable or improve in subsequent cycles.

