#### 1.2.1.2.3 Clinical pharmacokinetics

As of 28-Mar-2014, PK data were available from approximately 128 patients from the first-inhuman (FIH) study CLEE011X2101. Following oral dosing, LEE011 was rapidly absorbed with median Tmax ranging from 1 to 5 hours. LEE011 plasma exposure exhibited slightly over-proportional increases in exposure across the dose range tested (50 to 1200 mg), with no clear evidence of time-dependent auto-inhibition of its clearance mediated by CYP3A4. Steady-state was generally reached by Day 8 and the mean effective T1/2 based on accumulation ratio (i.e., T1/2,acc) ranged from 15.9 to 32.6 hours across the dose range tested.

The accumulation ratio based on AUC obtained in a dosing interval (Racc) across the studied doses ranged from 1.55 to 2.52. Details on the human pharmacokinetics of LEE011 can be found in the LEE011 Investigator Brochure.

A food effect study was conducted in 24 healthy subjects ([CLEE011A2111]). Compared to the fasted state, oral administration of a single 600 mg dose of LEE011 DiC with a high-fat, high-calorie meal decreased the rate of absorption of LEE011 resulting in a 23% decrease in Cmax (geometric mean ratio: 0.775; 90% confidence interval [CI]: 0.700, 0.858) and a median difference in Tmax of 2 hours. However, there was no effect on the extent of absorption of LEE011 as the overall exposure (AUCinf) was unaffected under fed conditions (geometric mean ratio: 0.994; 90% CI: 0.925, 1.070). A similar trend was observed for LEQ803, an active metabolite of LEE011, with a decrease in Cmax (102 to 69.7 ng/mL), a delay in median Tmax (2.50 to 6.00h), and no substantial effect on overall exposure (2970 to 2750 ng\*h/mL). Based on these data, LEE011 DiC can be taken without regard to meals.

A drug-drug interaction (DDI) study with ritonavir (a strong CYP3A4 inhibitor) and rifampicin (a strong CYP3A4 inducer) conducted in healthy subjects [CLEE011A2101] indicated that concurrent use of strong CYP3A4 inhibitors or strong CYP3A4 inducers may markedly affect LEE011 exposure and should be avoided. Details can be found in Section 5.1.5 of the Investigator Brochure.

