## Figure 4-1 Study Start-up Design

#### **4.1.1 Treatment phase**

Patients will continue to receive study treatment until disease progression (assessed by investigator per RECIST 1.1 or appropriate hematologic response criteria), unacceptable toxicity, death or discontinuation from study treatment for any other reason (e.g., withdrawal of consent, start of a new anti-neoplastic therapy or at the discretion of the investigator), otherwise known as End of Treatment. All patients who discontinue from study treatment due to disease progression must have their progression clearly documented.

Disease assessments (per RECIST 1.1 or appropriate hematological response criteria) will be performed every 8 weeks ( $\pm 4$  days) after first dose of study drug (Day 1 of every odd cycle), until disease progression or end of treatment, whichever occurs first. The frequency of disease assessment will be reduced to every 16 weeks after patients have completed 16 weeks on treatment. Scans will be assessed locally by the investigator.

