### **7.1.2 Treatment period**

Patients will be treated with ribociclib (600 mg, orally) until disease progression, unacceptable toxicity, death or discontinuation from the study treatment due to any other reason.

For details of safety and efficacy assessments, refer to [Table 7-1](#) and [Section 7.2](#).

- Visits and associated assessments that occur  $\pm$  4 days from the scheduled date (except for cycle 1 Day1 where no visit window is allowed) will not constitute protocol deviations.
- The cycle length is 28 days. Day 1 of subsequent cycles will be calculated from cycle 1, day 1.
- Disease Assessments (per RECIST or appropriate hematological response criteria) must be performed every 8 weeks ( $\pm$ 4 days) after first dose of study drug (Day 1 of every odd cycle), until disease progression or end of treatment, whichever occurs first. The frequency of disease assessment may be reduced to every 12 weeks for patients who have at least 4 post-baseline disease assessments and are clinically stable (except MM patients).
- Laboratory assessments performed as part of the screening evaluations, more than 4 days prior to the first dose of study treatment, must be repeated on the first dosing day.
- [REDACTED]

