### **7.1.3 End of treatment visit, including premature withdrawal and study discontinuation visit**

#### **7.1.3.1 End of treatment (EOT) visit**

Patients who completely discontinue study treatment should be scheduled for an End of Treatment (EOT) visit within 7 days following the date study treatment is permanently discontinued, at which time all of the assessments listed for the EOT visit will be performed. For details of assessments, refer to [Table 7-1](#). If the decision to withdraw the patient occurs at a regularly scheduled visit, that visit may become the EOT visit rather than having the patient return for an additional visit.

An End of Treatment Phase Disposition eCRF page should be completed, giving the date and reason for stopping the study treatment. If a study withdrawal occurs, or if the patient fails to return for visits, the investigator must determine the primary reason for a patient's premature withdrawal from the study and record this information on the End of Treatment Phase Disposition eCRF page.

End of treatment/Premature withdrawal visit is not considered as the end of the study.

For patients with a best response of SD or better who discontinue study treatment due to disease progression, an optional tumor sample should be obtained for genomic analysis.

For solid tumor patients with at least  $\geq$  20% reduction in overall tumor assessment (PR or better for hematological tumors) who discontinue study treatment due to disease progression,

[REDACTED]

[REDACTED]

At a minimum, all patients who discontinue study treatment, including those who refuse to return for a final visit, will be contacted for safety evaluations during the 30 days following the last dose of study treatment.

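### For patients without a prior QTcF of 481 ms or more, Cycle 1 Day 15 is the only timed routine ECG visit at steady state and peak level, so the protocol's change to the last available ECG can understate QTc prolongation (minor)

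*Protocol*

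**What the plan says.** Ribociclib is taken for 21 days of a 28-day cycle, and protocol 7.1.2 fixes the calendar: "Day 1 of subsequent cycles will be calculated from cycle 1, day 1". Day 1 of every cycle from the second on therefore nominally follows seven days without drug.

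Table 7-2 schedules ECGs as follows:

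- C1D1 and C1D15: pre-dose and 2, 4 and 6 h post-dose.
- C2D1 and C3D1: pre-dose and 2 h post-dose.
- After that: "For C4D1 and subsequent visits, the ECG will be measured only at pre-dose, except when clinically indicated".
- End of treatment (EOT) and unscheduled: at any time.

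A patient who reaches QTcF 481 ms or more gets additional ECGs 7 and 14 days after restarting. In Table 7-1, the ECG row is blank at C2D15.

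Protocol 1.2.1.2.1 says that QT changes show from Day 8 on, once steady state is reached, that they "are associated with the maximum drug levels between 1 to 8 h post-dose, and remain stable or improve in subsequent cycles".

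For analysis, protocol 10.5.3.1.3 specifies one descriptive ECG summary, the change from baseline to the last available result. SAP 5.5 specifies different tables: values by visit and time point, counts of notable values at any time (including increases above 30 and 60 ms), and shifts to the worst post-baseline category. SAP 2.3 lists departures from the protocol but none for ECGs, and SAP Section 1 refers the non-primary analyses to protocol Section 10.

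**The concern.** The protocol ties the QT effect to steady state and to the hours around peak level. After C1D15, no timed routine ECG meets both conditions. The last available tracing is then one of these:

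- For a patient still on treatment in Cycle 4 or later, nominally a Day 1 pre-dose ECG after the rest week.
- For a patient who progresses at a scheduled assessment, possibly that same visit. Assessments run "after first dose of study drug (Day 1 of every odd cycle), until disease progression or end of treatment, whichever occurs first" (protocol 4.1.1), and protocol 7.1.3.1 adds: "If the decision to withdraw the patient occurs at a regularly scheduled visit, that visit may become the EOT visit".
- Otherwise, an EOT "visit within 7 days following the date study treatment is permanently discontinued".

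SAP 2.5.6 counts everything up to 30 days after the last dose as on-treatment, so that rule does not set such tracings apart. QTc prolongation is an adverse event of special interest in SAP 5.1.5. A mean change computed on tracings of this kind can look reassuring because drug is absent, not because the effect is.

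**Working it through.** **Inputs.** The mean effective half-life (t) "ranged from 15.9 to 32.6 hours across the dose range tested", and the accumulation ratio ranged from 1.55 to 2.52 (both protocol 1.2.1.2.3, over 50 to 1200 mg; values at 600 mg are not given). Visit window: ±4 days (protocol 7.1.2). The model assumed here is one-compartment decline, with fraction remaining after h hours f(h) = 0.5^(h/t).

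**1. Reproduce the stated accumulation ratio.** Racc = 1/(1 − f(24)). At t = 15.9 h this is 1.54 (stated 1.55); at t = 32.6 h it is 2.50 (stated 2.52). Both agree within 1%. This shows that the stated half-lives and ratios match each other. It does not validate the extrapolation over a week, which uses the same model.

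**2. Gap before a Day 1 pre-dose ECG.** From the Day 21 dose to Day 29 is 8 × 24 = 192 h, or 192 − 24 = 168 h after the last steady-state trough.

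**3. Parent drug remaining, as a share of steady-state trough.**

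| Tracing | Hours after trough | t = 15.9 h | t = 32.6 h |
|---|---|---|---|
| Day 1 pre-dose, nominal | 168 | 0.07% | 2.8% |
| Day 1, 4 days early | 72 | 4.3% | 21.6% |
| Day 1, 4 days late, dosing held for the visit | 264 | 0.001% | 0.4% |
| Day 1, 4 days late, dosing restarted on the calendar (4 doses): 1 − f(96) | – | 98.5% | 87.0% |
| EOT 7 days after the last dose | 144 | 0.2% | 4.7% |
| EOT 1 day after a mid-cycle dose at steady state | 0 | 100% | 100% |

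**4. The 2 h ECGs on C2D1 and C3D1.** They follow one dose after the rest week. Exposure over that dosing interval, relative to steady state, is 1/Racc: 1/2.52 = 40% to 1/1.55 = 65%. This is an AUC ratio, not a 2 h concentration.

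**5. Level at C1D15.** After 14 daily doses the level is 1 − f(336), above 99.9% of steady state for both half-lives.

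**6. Count of timed routine time points through Cycle 6.** C1D1 4 + C1D15 4 + C2D1 2 + C3D1 2 + C4 to C6 3 = 15. Four are at steady state, all on C1D15, and three of those are in the 1 to 8 h window. Of the 7 after C1D15, 5 are pre-dose after the rest week, 2 follow a single dose, and none is at steady state.

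**7. How common is stopping for progression?** In phase I, 96 of 111 discontinuations were for progression (96/111 = 86%). That study mixed doses and schedules, and the figure gives the reason for stopping, not the timing of the ECG. It shows only that the scheduled-assessment route is plausible.

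**The case against.** The case on the other side is strong on consequence.

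- **The SAP already reports the right quantities.** The C1D15 readings appear by time point, increases are counted whenever they occur, and shifts go to the worst value. This stands, and it is why the point is minor. That the last-available table will be produced at all is inferred from SAP Section 1 and the silence of SAP 2.3.
- **The protocol also flags and lists notable values.** A high C1D15 reading would be visible under 10.5.3.1.3 alone. This stands.
- **Front-loading is defensible.** Phase I found later changes stable or improving, patients at 481 ms or more get extra ECGs, and others can have one when clinically indicated. This stands in part. It supports asking for one repeat peak reading and no more.
- **The residual figures are model-based.** An effective half-life derived from accumulation is carried over a week. The figures also cover parent drug only, although protocol 1.2.1.1.3 says that LEQ803 likely contributed to the QT effect in dogs. This stands; residual QT-active exposure is not known.

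A reader might infer that the last available ECG will usually be off drug. The documents do not show this: EOT and unscheduled ECGs may be taken at any time, suspected progression is assessed promptly (protocol 7.2.1), and no EOT timing is given. Nor can every Day 1 pre-dose row be called off drug, as the late-visit case in the table shows. A reader might also infer that the trial will fail to report QTc prolongation. SAP 5.5 rules that out for effects captured on a tracing. What it cannot recover is a steady-state peak effect after C1D15 that no scheduled ECG measured.

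**Conclusion.** The point holds at minor severity. In patients without a prior QTcF of 481 ms or more, C1D15 is the only timed routine visit that meets both of the protocol's own conditions for seeing a QT effect. The ECG summary specified in protocol 10.5.3.1.3 can therefore rest on a post-rest-week or post-discontinuation tracing and understate prolongation. Its frequency cannot be estimated from the documents. The size of the washout rests on the one-compartment assumption and nominal visit timing, and on parent drug alone. The primary endpoint is unaffected. What remains is a mismatch between protocol and SAP over one weak summary, and the lack of a second scheduled steady-state peak reading.

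**What to change.** **(a) Analysis.** In protocol 10.5.3.1.3, replace change to the last available ECG with change from baseline to C1D15 (each time point) and to the worst post-baseline value. Add that continuous change-from-baseline summary to SAP 5.5, which at present gives values, counts and category shifts, and record the departure in SAP 2.3. Label Day 1 pre-dose rows from Cycle 2 on as *nominally post-rest-week*, not as off drug. The cost is one replaced summary and a row label, all from data already collected. Actual time since last dose is not needed; it would be hard to derive, because SAP 3.5.1.3 notes that dosing records include the planned breaks and that cycle start dates are not collected.

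**(b) Collection, for this schedule or its reuse.** Move the C3D1 2 h post-dose ECG to 2 h post-dose at the existing C2D15 visit, editing both Table 7-2 and the ECG row of Table 7-1. The C2D1 2 h ECG stays as the check after restarting. The total remains 15 time points through Cycle 6, with 5 instead of 4 at steady state. One first-dose reading is lost and C2D15 gains a 2 h wait; there is no new visit and no extra ECG. It repeats the peak reading once and adds none from Cycle 3 on. Because enrolment closed in May 2015, its practical value lies in further use of the schedule.

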#### 7.2.2.6.2 Cardiac imaging - MUGA (multiple gated acquisition) scan or echocardiogram

[figure not shown]
MUGA (multiple gated acquisitions) scan or echocardiogram (ECHO) will be used to assess LVEF at screening and during the treatment phase as clinically indicated to assess signs or symptoms of cardiotoxicity. In case of clinically significant abnormalities, they should be reported on the Adverse Events eCRF.

In case a patient develops left ventricular systolic dysfunction while on study treatment dose adjustment guidelines described in [Section 6.3](#) must be followed.

#### 7.2.3 Pharmacokinetics

Not Applicable.

### **7.2.5 Other assessments**

No additional tests will be performed on patients entered into this study.

## **8 Safety monitoring and reporting**

### **8.1 Adverse events**

[figure not shown]
#### **8.1.1 Definitions and reporting**

An adverse event (AE) is defined as the appearance of (or worsening of any pre-existing) undesirable sign(s), symptom(s), or medical condition(s) that occur after patient's signed informed consent has been obtained.

For patients who sign the ICF, all AEs will be captured in the AE eCRF from time of signature through 30 days after permanent study treatment discontinuation. For patients who fail the screening, only SAEs will be captured in the AE eCRF page.

Abnormal laboratory values or test results occurring after informed consent constitute adverse events only if they induce clinical signs or symptoms, are considered clinically significant, require therapy (e.g., hematologic abnormality that requires transfusion or hematological stem cell support), or require changes in study medication(s).

Adverse events that begin or worsen after informed consent should be recorded in the Adverse Events eCRF. Conditions that were already present at the time of informed consent should be

recorded in the Medical History eCRF. Adverse event monitoring should be continued for at least 30 days following the last dose of study treatment. Adverse events (including lab abnormalities that constitute AEs) should be described using a diagnosis whenever possible, rather than individual underlying signs and symptoms. When a clear diagnosis cannot be identified, each sign or symptom should be reported as a separate Adverse Event.

Adverse events will be assessed according to the Common Terminology Criteria for Adverse Events (CTCAE) version 4.03. If CTCAE grading does not exist for an adverse event, the severity of mild, moderate, severe, and life-threatening, corresponding to Grades 1-4, will be used. CTCAE Grade 5 (death) will not be used in this study; rather, information about deaths will be collected through a Death form.

The occurrence of adverse events should be sought by non-directive questioning of the patient (subject) during the screening process after signing informed consent and at each visit during the study. Adverse events also may be detected when they are volunteered by the patient (subject) during the screening process or between visits, or through physical examination, laboratory test, or other assessments. As far as possible, each adverse event should be evaluated to determine:

1. The severity grade (CTCAE Grade 1-4)
2. Its duration (Start and end dates)
3. Its relationship to the study treatment (Reasonable possibility that AE is related: No, Yes)
4. Action taken with respect to study or investigational treatment (none, dose adjusted, temporarily interrupted, permanently discontinued, unknown, not applicable)
5. Whether medication or therapy taken (no concomitant medication/non-drug therapy, concomitant medication/non-drug therapy)
6. Outcome (not recovered/not resolved, recovered/resolved, recovering/resolving, recovered/resolved with sequelae, fatal, unknown)
7. Whether it is serious, where a serious adverse event (SAE) is defined as in [Section 8.2.1](#)

All adverse events should be treated appropriately. If a concomitant medication or non-drug therapy is given, this action should be recorded on the Adverse Event eCRF.

Once an adverse event is detected, it should be followed until its resolution or until it is judged to be permanent, and assessment should be made at each visit (or more frequently, if necessary) of any changes in severity, the suspected relationship to the study treatment, the interventions required to treat it, and the outcome.

Progression of malignancy (including fatal outcomes), if documented by use of appropriate method (as per RECIST 1.1 criteria for solid tumors or as per Cheson's guidelines for hematological malignancies), should not be reported as a serious adverse event or adverse event.

Adverse events separate from the progression of malignancy (example, deep vein thrombosis at the time of progression or hemoptysis concurrent with finding of disease progression) will be reported as per usual guidelines used for such events with proper attribution regarding relatedness to the drug.

